Baseline assessments will include:

- 1) Return of the 3-day voiding diary;
- 2) OABq questionnaire;
- 3) TENS (transcutaneous electrical nerve stimulation) protocol instructions provided to subjects.

Study staff will schedule subject's implantation procedure to follow baseline assessments. All subjects who continue to meet the inclusion and exclusion criteria after baseline assessments will be enrolled in the study.

Pivotal Study of Subcutaneous Tibial Nerve Stimulation with eCoin[®] for Urgency Urinary Incontinence.

3-4-7 TENS Protocol

One secondary purpose of this trial is to ascertain whether there is a relationship between responders to TENS and responders to eCoin therapy. Therefore, at baseline, subjects will be sent home with a TENS unit and instructions to perform TENS of the tibial nerve twice daily for seven days. The electrical paradigm will be preset to match the electrical paradigm of eCoin (pulse width of 0.2 ms and frequency of 20 Hz), but the subject will set the amplitude of stimulation to the upper level of comfort. Subjects should perform one thirty minute session in the morning and one in the evening for 7 days (total of 14 sessions). Subjects will be asked to complete a voiding diary in the last three days of the TENS protocol. This TENS protocol will occur after the baseline visit but before the implantation visit. Subject eligibility is not affected by response or lack of response to the TENS protocol.

Study staff will schedule subject's implantation procedure to follow collection of three-day diary completed during the last three days of the TENS protocol.

3-4-8 Implantation of Subcutaneous Neuromodulation System

An implant procedure is to be completed following, but no later than, 28 days from the baseline visit. The eCoin[™] system will be implanted in accordance with the procedures outlined in the Surgical Implant Manual set forth in [Attachment 4-2 for Manuals and Labels](#). The implant procedure is conducted as an outpatient procedure under local anesthesia for subcutaneous placement. An incision site healing check will be performed 2 weeks post implant. Subjects will be provided a minimum of 4 weeks for healing prior to activation of the system.

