Original Application for an Investigational Device Exemption

Pivotal Study of Subcutaneous Tibial Nerve Stimulation with eCoin[®] for Urgency Urinary Incontinence.

This open label, single-arm study will evaluate eCoin[™]'s effectiveness in reducing episodes of urgency urinary incontinence. The proportion of subjects achieving at least a 50% reduction from baseline in the number of urgency urinary incontinence episodes will be reported.

Valencia considered a controlled trial against an approved drug or placebo. Such a trial would be very difficult to blind. Recruitment to a trial comparing eCoin[™] to Interstim would be difficult because many people are unwilling to use Interstim.

Pivotal Study of Subcutaneous Tibial Nerve Stimulation with eCoin[®] for Urgency Urinary Incontinence.

3-9-3-2 Analysis Sets

Effectiveness analyses will be generated for all analysis populations described below. Safety data will be reported on all enrolled subjects who undergo a procedure for implantation of the study device

- 1) Intent-to-Treat (ITT): All enrolled subjects who undergo a procedure for implantation of eCoin[™]. This is the primary analysis population for the safety and effectiveness analyses.
- 2) Modified Intent-to-Treat (mITT). All subjects in the ITT population meeting all eligibility criteria.
- 3) OAB drug-free. All subjects in the mITT population who took no medication for OAB during the study period.
- 4) Per-protocol (PP): The subset of OAB drug-free subjects excluding all subjects with any other major protocol violation. The SAP will define major protocol deviations.
- 5) Responders: Subjects who respond to treatment, defined as those who achieve at least a 50% reduction in the number of urgency urinary incontinence episodes from baseline to 48 weeks post-activation.
- 6) TENS Cohort Analysis (TNS): The subset of ITT subjects less any patients who do not respond to the TENS protocol where response is defined as a 30% reduction in urgency urinary incontinence episodes or a 30% reduction in urgency episodes from baseline after 7 days of TENS.
- 7) Long-term Completers: All mITT subjects who attend a particular visit. This is the primary analysis population for the effectiveness and safety analyses performed at 2 and 3 years post-activation for subjects who consent to extended follow-up.

The SAP may define additional analysis sets of subjects.

3-9-3-3 Planned analyses

3-9-3-3-1 Primary Effectiveness Outcome

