The primary effectiveness outcome is achieving at least a 50% reduction from baseline in the number of urgency urinary incontinence episodes per 24 hours on a 3 day voiding diary after 48 weeks of eCoin[™] tibial nerve stimulation.

The proportion of responders along with its 2-sided 95% exact Clopper-Pearson confidence interval will be summarized after 48 weeks of therapy.

3-9-3-3-2 Key Secondary Effectiveness Outcome

The key secondary effectiveness outcome is achieving at least a 50% reduction from baseline in the number of urgency urinary incontinence episodes per 24 hours on a 3 day voiding diary after 24 weeks of eCoin[™] tibial nerve stimulation.

Pivotal Study of Subcutaneous Tibial Nerve Stimulation with eCoin[®] for Urgency Urinary Incontinence.

The proportion of subjects with at least 50% reduction from baseline along with its 2-sided 95% exact Clopper-Pearson confidence interval will be summarized after 24 weeks of therapy.

3-9-3-3-3 Primary Safety Outcome

The primary safety outcome is device-related adverse events from implantation to 52 weeks after implantation of eCoin[™].

All device-related adverse events up to 52 weeks after implantation of eCoin[™] will be summarized by preferred term. Tabulations of these data will include the number of subjects exposed and the number of subjects with at least one device-related adverse event.

3-9-3-3-4 Key Secondary Safety Outcome

The key secondary safety outcome is device-related adverse events 28 weeks after implantation of eCoin[™].

All device-related adverse events up to 28 weeks after implantation of eCoin[™] will be summarized by preferred term. Tabulations of these data will include the number of subjects exposed and the number of subjects with at least one device-related adverse event.

3-9-3-3-5 Secondary Outcomes

The secondary outcomes listed in this section are based on data after 24 and 48 weeks from activation (28 and 52 weeks after implantation). These outcomes, which are for descriptive purposes, will not be formally analyzed statistically. The SAP will describe in detail analyses of the secondary outcomes.

- Achieving 75% improvement in the number of urgency urinary incontinence episodes per 24 hours on a 3 day voiding diary.
- Achieving 100% improvement in urgency urinary incontinence episodes (“Dryness”) per 24 hours on a 3 day voiding diary.
- Reduction from baseline in the number of urgency urinary incontinence episodes per 24 hours on a 3 day voiding diary.

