2.4. Transcutaneous electrical nerve stimulation (TENS) protocol

A secondary motivation for this trial is to ascertain whether there is a relationship between responders to transcutaneous electrical nerve stimulation (TENS) and responders to eCoin™ therapy. Subjects will receive a TENS unit at baseline with instructions to perform TENS of the tibial nerve twice daily for seven days. Subjects will be asked to complete a voiding diary in the last three days of the TENS protocol. This TENS protocol will occur after the baseline visit but before implantation with eCoin™. Response or lack of response to the TENS protocol does not affect subject eligibility.

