a. Weight, height, body mass index, temperature, pulse rate, respiratory rate, and blood pressure will be assessed at the screening visit. Only pulse rate, temperature, and blood pressure will be collected at subsequent visits. In addition, respiratory rate will be collected at visit 4 and visit 13.
b. For visits involving a 3-day diary, the diary should be completed over 3 consecutive days during the 7 days prior to each indicated visit. The site should give patients a telephone call to remind them of the diary requirement at least 3 days prior to each follow-up visit.
c. Visit 3 (Implant procedure) will assess satisfaction and impression of improvement relative to the TENS therapy. All other visits will be relative to the eCoin™ neuromodulation device.

5. Analysis populations

Effectiveness analyses will be generated for all analysis populations described below. Safety data will be reported on all enrolled subjects who undergo a procedure for implantation of the study device.

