7.2. Baseline

Baseline efficacy measures will be defined as the last measure taken up to and including the baseline visit (Visit 2). Baseline safety measures will be defined as the last measure taken prior to device implantation.

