9.2. Patient surveys

Three separate patient surveys will be administered several times over the course of the study.

9.2.1. *Overactive Bladder Symptom Quality of Life Questionnaire (OABq)*

The OABq is a 33-item questionnaire that measures quality of life. It contains a “symptom bother” subscale and a Health-Related Quality of Life (HRQoL) subscale. Each question is scored using a six-point scale, with higher scores indicating more severe symptoms or poorer

quality of life. The scores are summed separately for the 2 subscales and transformed into 2 composite scores ranging from 0 to 100.

9.2.2. *Patient reported satisfaction assessment*

The patient reported satisfaction assessment will rate each subject's level of satisfaction with the eCoin™ neuromodulation system on a scale of one to five, where one is "Not at all satisfied" and five is "Completely satisfied." The satisfaction assessment will ask the following three questions:

- "How satisfied is the subject with the eCoin device itself?"
- "How satisfied is the subject with the programming of the device?"
- "How satisfied is the subject with the stimulation of the device?"

9.2.3. *Patient Global Impression of Improvement (PGI-I) questionnaire*

The PGI-I questionnaire will assess patient-reported overactive bladder condition on a scale of one to seven. The questionnaire inquires "Compared to how the subject's urinary leakage was before treatment, subject now reports that he or she feels", with responses ranging from one ("Very much better") to seven ("Very much worse").

10. **Efficacy analyses**

10.1. **Primary efficacy analysis**

This open label, single-arm study will evaluate the effectiveness of eCoin™ in reducing episodes of UUI. The primary efficacy outcome is achieving at least a 50% reduction from baseline in the number of UUI episodes per 24 hours on a 3-day voiding diary after 48 weeks of eCoin™ tibial nerve stimulation. The proportion of subjects achieving at least a 50% reduction along with its 2-sided 95% exact Clopper-Pearson confidence interval will be summarized for subjects in the ITT population.

Because this study is investigating an implanted device, nearly all implanted subjects are expected to have data on the primary endpoint. Careful clinical planning that minimizes

subject dropouts will be implemented. Any missing data for the primary outcome will be handled as follows:

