10.4. Sensitivity and additional analyses

The primary and secondary efficacy analyses will be repeated for all analysis populations (mITT, OAB drug-free, Per-protocol, Responders, and TENS cohort analysis). These analyses will also be repeated for the mITT analysis population excluding any subjects enrolled but not meeting all eligibility criteria who were subsequently re-baselined to correct any eligibility violations.

Additional sensitivity analyses may be conducted to evaluate different methods of handling missing data, such as tipping point, best-case, and worst-case scenario analyses.

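### TENS response and eCoin response are both measured as falls from the same Visit 2 diary, so TENS responders tend to show a higher eCoin response even if TENS predicts nothing

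*Protocol*

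**What the plan says.** Protocol 3-4-7 gives the TENS week as one secondary purpose of the trial: to "ascertain whether there is a relationship between responders to TENS and responders to eCoin therapy". SAP 2.4 calls it a secondary motivation and fixes the timing: "This TENS protocol will occur after the baseline visit but before implantation with eCoin™". The TENS diary covers the last three days of that week.

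The TENS cohort (Protocol 3-9-3-2 item 6, SAP 5.6) is the ITT population without the TENS non-responders, where "response is defined as a 30% reduction in urgency urinary incontinence episodes or a 30% reduction in urgency episodes from baseline". For eCoin, SAP 10.1 states: "The primary efficacy outcome is achieving at least a 50% reduction from baseline in the number of UUI episodes per 24 hours", assessed at week 48.

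SAP 7.2 sets one reference for every efficacy measure: "Baseline efficacy measures will be defined as the last measure taken up to and including the baseline visit (Visit 2"). The only analysis specified for the TENS cohort is in SAP 10.4: "The primary and secondary efficacy analyses will be repeated for all analysis populations (mITT, OAB drug-free, Per-protocol, Responders, and TENS cohort analysis"). Neither document provides a second pre-TENS diary, names a comparison with TENS non-responders, or warns about the common baseline.

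**The concern.** Both responses are ratios with the same noisy denominator. A subject whose three baseline days were unusually bad, by chance or in a flare, is more likely to meet the 30% criterion on TENS and the 50% criterion at week 48, whatever either therapy does. A subject with an unusually good baseline is less likely to meet either. The two responses are therefore positively associated by construction.

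The question the TENS week is meant to answer is whether the two responses are related. The planned repeat in the TENS cohort, read beside the ITT rate, leans towards yes when the truth is no. A TENS subgroup under the exploratory analyses of SAP 10.4.1 would carry the same artefact. At stake is a mistaken belief that a week of TENS identifies who will benefit from the implant.

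**Working it through.** **Inputs from the documents.** TENS criterion: 30% fall in UUI or in urgency episodes (Protocol 3-9-3-2). eCoin criterion: at least 50% fall in UUI (SAP 10.1). Common Visit 2 baseline (SAP 7.2). Entry: at least one UUI episode on each of three diary days (Protocol 3-3-2-2-1). Target N = 120 (SAP 6). The plan has no figure for the TENS-eCoin association to reproduce; its power figures concern the ITT test and do not enter here.

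**Mechanism by hand.** Let B, T and E be the three-day UUI totals at baseline, on TENS and at week 48. On the UUI criterion, TENS response is T ≤ 0.7B and eCoin response is E ≤ 0.5B. Assume a true rate of 3/day (9 per diary), Poisson counts, TENS inert, and eCoin halving the rate (mean 4.5).

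- B = 12 by chance: the thresholds are T ≤ 8 and E ≤ 6. P(Poisson(9) ≤ 8) = 0.456; P(Poisson(4.5) ≤ 6) = 0.831.
- B = 6 by chance: the thresholds are T ≤ 4 and E ≤ 3. P(Poisson(9) ≤ 4) = 0.055; P(Poisson(4.5) ≤ 3) = 0.342.

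Mix these two kinds of subject equally:

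- eCoin response in TENS responders: (0.456×0.831 + 0.055×0.342)/(0.456 + 0.055) = 0.78.
- In TENS non-responders: (0.544×0.831 + 0.945×0.342)/(0.544 + 0.945) = 0.52.

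All these subjects have the same true rate and the same true effects. The difference comes only from B.

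**Simulation with varying eCoin effects.** Assumptions, none from the documents: lognormal subject rates with mean 2, 4 or 6 UUI/day and CV 0.6; between-diary CV 0, 0.2 or 0.4; Poisson days; the entry criterion applied; about 2 urgency episodes per UUI, with both limbs of the TENS definition used; TENS either inert or with median multiplier 0.8 (log-SD 0.4); eCoin effect log-SD 0.8, drawn independently of TENS; overall response set at 40%, 55% or 70%. That is 3×3×2×3 = 54 scenarios.

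- TENS responders did better in all 54. The gap over non-responders was 5.2 to 16.9 points and the lift over ITT 2.7 to 10.6 points.
- Central case (4/day, CV 0.2, TENS inert): 33.2% are TENS responders, with eCoin response 63.8% against 50.6%. Check: 0.332×63.8 + 0.668×50.6 = 55.0, the ITT rate. Gap 13.2, lift 8.8, odds ratio (0.638/0.362)/(0.506/0.494) = 1.72.
- Central case with eCoin log-SD 1.5: gap 8.0, lift 5.3. With log-SD 0.3, close to a common effect: gap 20.2, lift 13.4.
- A second model (gamma rates, 2-5/day, between-diary CV 0-0.5, eCoin log-SD 0.8-1.2) gave gaps of 8 to 18 points and odds ratios of 1.4 to 2.1.

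**Same effect in every subject.** With eCoin halving every rate, TENS inert and the urgency limb included, the lift over ITT is about 9 to 17 points and the odds ratio about 2.4 to 3.0.

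**Is the shared baseline the cause?** With an almost noise-free diary (200 episodes/day, no between-diary variation) the gap falls to 0.4 points. In the 54 scenarios, measuring TENS response against a second, independent baseline diary leaves −0.3 to +1.8 points (at most 2.2 with the UUI limb alone).

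**What one trial would show.** Central case, about 40 TENS responders and 80 non-responders: SE = √(0.638×0.362/40 + 0.506×0.494/80) = 0.094. An expected gap of 13.2 points is thus 1.4 standard errors. A two-sided 5% comparison would be nominally significant in about 27% of such trials (9% to 44% across the scenarios examined), although TENS predicts nothing.

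**Does adjustment cure it?** Adjusting eCoin response for the baseline count leaves an odds ratio of about 1.6 to 2.8 under no relationship. The observed count does not separate a high true rate from a chance-high diary.

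**The case against.** The size is uncertain and easily overstated. If eCoin is assumed to multiply every subject's rate by exactly 0.5, everyone sits on the 50% threshold and baseline noise decides who responds. Letting effects vary roughly halves the excess in the odds ratio. This stands, so the range for varying effects comes first and the common-effect figures are an upper end. The urgency limb dilutes the coupling only slightly, because it comes from the same diary. Re-baselined subjects (SAP 2.5) may have different references for the two responses.

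The weight is also limited. The TENS-eCoin relationship is not among the objectives in Protocol 3-5 or SAP Table 1, TENS response does not affect eligibility, and the cohort is one of several repeats. This also stands.

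A reader might infer three stronger things that the documents do not support:

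- That TENS responders are bound to do better in this trial. The bias is in expectation; with varying effects, responders came out at or below non-responders in about 2% to 23% of simulated trials of 120.
- That the sponsor plans to use TENS to select implant candidates. No such use, and no responder versus non-responder test, is specified.
- That the primary result is biased by this. The ITT test against 40% does not use TENS response.

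What remains is that the plan states the question and offers only an analysis that leans towards one answer.

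**Conclusion.** The point holds as a bias in expectation on a secondary question. The common Visit 2 reference is explicit in the documents, and the direction was the same in every scenario. The lift over ITT is about 3-11 points and the gap over TENS non-responders about 5-18 points when eCoin effects vary between subjects; the lift reaches about 9-17 points (odds ratio about 2.4-3.0) with a common effect. These sizes rest on assumed rates (2-6 UUI/day), between-diary CV (0-0.5), urgency-to-UUI ratio and effect heterogeneity, none of which the documents give. The primary conclusion is untouched. Label: cheap improvement.

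**What to change.** In SAP 5.6 and 10.4:

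(a) State that the TENS cohort rate is selected on the baseline diary that also defines eCoin response, that it is not comparable with the ITT rate, and that it will not by itself be used to claim that TENS response predicts eCoin response.

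(b) Add a sensitivity table relating the Visit 3 PGI-I to week-48 diary response, with the PGI-I cut-off fixed in advance. These data are already collected: "Visit 3 (Implant procedure) will assess satisfaction and impression of improvement relative to the TENS therapy" (SAP Exhibit 1, footnote c). State its limits beside it. It removes diary counting error but not a true flare before baseline, because the question compares leakage with the time before treatment (SAP 9.2.3), and it is coarser and subjective.

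Two tempting alternatives should not be adopted. Simple adjustment for the baseline count does not remove the artefact. A rule that claims a relationship when the observed odds ratio exceeds a simulated expected value sets a point estimate against an expectation, so it would be met in roughly half of trials with no relationship; that expected value also depends on effect heterogeneity, which diary means and variances do not supply.

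The cost is a few sentences and one table, with no new visits and no change to the primary analysis. SAP 7.3 allows the revision before database lock.

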Valencia Technologies Corporation

Pivotal Study of Subcutaneous Tibial Nerve Stimulation with eCoin™ for Urgency Urinary Incontinence

**Statistical Analysis Plan
Version 3.0
August 28, 2019**

Prepared by:
Statistics Collaborative, Inc.

[figure not shown]
Valencia Technologies Corporation

Protocol G170301 Statistical Analysis Plan

August 28, 2019

Version 3.0

Prepared by: Statistics Collaborative, Inc.

[figure not shown]
Author: 
[name], MS
Biostatistician II

Date: 28-AUG-19

Author: 
[name]
President

Date: 28-Aug-19

Approved by: Valencia Technologies Corporation

[name], LLM
Chief Executive Officer

Date: 28-AUG-19

Synopsis

Protocol title	A multicenter, single-arm study designed to evaluate the safety and effectiveness of eCoin™ tibial nerve stimulation in subjects with urgency urinary incontinence (UUI)
Treatment assignment	Up to 135 subjects, with a target of 120 subjects, who meet all inclusion and exclusion criteria will be enrolled to participate. All subjects will be scheduled to receive the investigational therapy, eCoin™.
Study design	After screening and baseline assessments, the eCoin™ neuromodulation device will be implanted subcutaneously in the right or left leg of subjects. After a 4 week implant healing period, all subjects will have a programming visit where the device will be activated (turned on). Subjects will be followed for 48 weeks post-device activation (equivalent to 52 weeks post-implantation). All subjects will be explanted after the final study visit at 48 weeks post-activation.
Analysis population	The primary analysis population for the effectiveness and safety analyses will be the intent-to-treat (ITT) population: all enrolled subjects who undergo a procedure for implantation of eCoin™.
Primary efficacy outcome	Achieving at least a 50% reduction from baseline in the number of urgency urinary incontinence episodes per 24 hours on a 3-day voiding diary after 48 weeks of eCoin™ tibial nerve stimulation
Key secondary efficacy outcome	Achieving at least a 50% reduction from baseline in the number of urgency urinary incontinence episodes per 24 hours on a 3-day voiding diary after 24 weeks of eCoin™ tibial nerve stimulation
Primary safety outcome	Device-related adverse events from implantation to 52 weeks after implantation of eCoin™
Key secondary safety outcome	Device-related adverse events from implantation to 28 weeks after implantation of eCoin™
